5.0 Analysis of Safety

The following describes the statistical analysis of safety data.

Adverse Events

Prior to analysis, all AEs will be coded using the Medical Dictionary for Regulatory Activities (MedDRA). A treatment-emergent adverse event (TEAE) is any AE that occurs after the start of treatment. All TEAEs will be summarized by the treatment at the time of onset. Counts and percentages will be presented by treatment for each observed system organ class (SOC) and preferred term (PT) as defined in MedDRA. Summaries by level of severity and relationship to treatment will be presented by treatment at the time of occurrence. Listings of all deaths, serious AEs (SAEs), and discontinuations due to AE will be provided.

An overall summary table will provide the highest relationship and maximum severity observed per subject, as well as the counts of patients who: discontinued early due to an AE, experienced death, or had at least one SAE.

Laboratory Tests

For each laboratory parameter, descriptive statistics will be presented for the observed value and change from baseline (CFB) by treatment, where CFB is the change from the previous assessment. The frequency and percentage of patients who experience

abnormal (i.e. outside of reference ranges) laboratory values will be presented by treatment and time point.

Concomitant Medications

A table of the WHO-coded medications will be constructed by treatment given in the study period (amifampridine or placebo) and overall with medications summarized by level 4 Anatomical Therapeutic Chemical (ATC) term and Preferred Term. The number and percent of patients on each drug will be summarized. A data listing for all concomitant medications will be provided.

Vital Signs

Summary statistics (mean, median, sample size, standard deviation, minimum, and maximum) will be computed on the raw and change from baseline values for each vital sign parameter by time point, for each treatment. The screening time point will serve as baseline. If there are multiple vital signs taken at any time point, then the latest set of vital signs will be used for the analysis. All vital sign data will be listed.

ECG Results

ECG parameters will be summarized with descriptive statistics by time point and treatment sequence. A shift table of investigator classification of the ECG will be created showing Normal/Normal, Normal/Abnormal, Abnormal/Normal, and Abnormal/Abnormal frequencies by time point using the screening value as the baseline. All ECG data will be listed.

Physical Examination Findings

All Physical Examination data will be listed as shown in Appendix B.

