After Day 8 in-clinic evaluations, patients will return to open-label study drug, through Day 21 (same dose and frequency as at the end of run-in), as prescribed by investigator and dispensed by research pharmacist. No dose adjustments may occur. Patients who were on stable dose of amifampridine phosphate with history of meaningful improvement prior to randomization in CMS-001, will be returned to the same stable dose and frequency during the re-stabilization period.

Period 2 (Days 22-29) (+1 day)

Study medication will be dispensed by the site pharmacist on the last day of the Stabilization Period (i.e. Day 21), according to the randomization schedule. **Patients will start the blinded study medication only after completion of all of the Day 22 assessments, while taking open-label medication, 40 minutes before starting assessments.**

Per the crossover design, patients will receive the double-blind study medication (either amifampridine phosphate tablets or placebo tablets) during Period 2, for 8 days (Day 22 – 29) as an outpatient with a dose of the same medication on the day of scheduled study visit (Day 29), administered by study personnel in the clinic, to facilitate efficacy assessments, under double-blind conditions. If the patient is on a BID or TID regimen during Period 2, the Day 29 assessments should occur after the same dose that corresponds to when assessments were done on Day 0. Any unused portion of dispensed drug will be returned to the site before enrolling the patient in the expanded access program and dispensing open-label drug.

Table 3. Schedule of Events

Study Assessment or Event ^d	Screening ^{qr}	Run-in (up to 4 weeks) ^a		Period I		Re-stabilization		Period II
		Start of Run-in	Last Visit	Days 1-8		Days 9-21		
		Days -14 to -1	Day 1	Day 0 ^{b, c}	Days 1-7	Day 8 ^c (+1 d)	Days 9-20	Day 21 ^c (+1 d)
Informed consent ^e	X							
Inclusion/exclusion criteria	X		X					
Randomization			X					
Medical history	X		X ^f					
CMS genetic testing ^g	X							
Complete physical exam ^h	X							
Abbreviated physical exam ⁱ			X		X		X	
Vital signs	X		X		X		X	
12-Lead ECG	X							
Clinical laboratory tests	X		X		X			
Pregnancy test ^j	X		X				X	
IP dispense		X	X ^k		X ^l		X ^k	X
IP Administration ^{m,p}		X		X ⁿ	X ⁿ	X ⁿ	X ⁿ	X ⁿ

Table 3. Schedule of Events

Study Assessment or Event ^d	Screening ^{qr}	Run-in (up to 4 weeks) ^a		Period I		Re-stabilization		Period II
		Start of Run-in	Last Visit	Days 1-8		Days 9-21		

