15.3 Adverse Events

All treatment-emergent adverse events (TEAEs) will be summarized by the treatment at the time of onset. Counts and percentages will be presented by treatment for each observed system organ class (SOC) and preferred term (PT) as defined in MedDRA. Summaries by level of severity and relationship to treatment will be presented by treatment at the time of occurrence. Listings of all deaths, SAEs, and discontinuations due to AE will be provided.

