1.2 Study Procedures

Amifampridine phosphate oral dosing using 10 mg tablets starts on Day 1 of the open-label run-in and patients were titrated upward every 3 to 4 days, per guidelines in the protocol and at the discretion of the investigator, for up to 4 weeks, with 1 week of stable dose and frequency at the end of the run-in period before being randomized. Dosing and/or dosing frequency was increased or decreased by the investigator during the run-in phase prior to the last week of stable dosing. Per the protocol, randomization could only occur after the patient has been on a stable dose and dosing frequency for at least 7 days.

At the end of their Period 1 randomization treatment, patients will return to open-label amifampridine phosphate for 14 days between Periods 1 and 2 at the same dose and

dosing frequency established in the run-in phase. No dose adjustments were allowed during this re-stabilization period.

After completing Period 2, (the completion point for this trial) patients were eligible for an open-label amifampridine phosphate treatment protocol (CMS-002).

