4.2 Analysis of Efficacy

4.2.1 Analysis of Primary Efficacy

Summary statistics for the SGI Day 0 assessment (baseline for period 1), SGI Day 8 assessment, and the corresponding change from baseline (CFB₁) will be presented by treatment and by treatment within mutation type (pre- vs. post-synaptic, see Table 2.2-1 above) as period 1. A Mann-Whitney-Wilcoxon test for equality of the CFB₁ in the two treatments in Period 1 will be presented. Summary statistics for the SGI Day 21 assessment (baseline for period 2), SGI Day 29 assessment, and the corresponding change from baseline (CFB₂) will also be presented by treatment and treatment within mutation type as period 2. Also, the change in CFB from Period 1 to Period 2 will be computed. This value estimates

$$\tau_1 - \tau_2$$

where τ_1 represents the treatment effect of the period 1 Investigational Product (IP) and τ_2 represents the treatment effect of period 2 IP. A Mann-Whitney-Wilcoxon test of the hypothesis that the above parameter is the same in both treatment sequences will be provided. Note that this is a nonparametric version of the treatment main effect in a linear model without carryover effects.

A mixed effects linear model will be fit to the data with SGI raw scores as the response. The model will include fixed effect terms for treatment, period, age group (2 to less than 6, 7 to less than 12, and 12 to less than 17 years of age, 17 years and over), mutation type and sequence*period, where sequence corresponds to the order in which the subject received treatments, and a random effect for subject. The LSMeans for the treatment groups will be calculated and provided, as will the estimated difference along with a 95% confidence interval for this difference and a formal hypothesis test that the difference in the means is 0.

Special care must be taken in crossover designs to ensure that there is not significant carryover effect; however, the pharmacological properties of amifampridine are such that

having a 12-day washout period should minimize any unequal carryover effects in the analysis.

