A mixed effects linear model will be fit to each of the MFM datasets described above with percent outcome or individual item scores (as appropriate for each dataset) as the response variable. The model will include fixed effect terms for treatment, period, age group (2 to less than 6 years, 7 to less than 12 years, 12 to less than 17 years of age, and 17 years of age and above), genetic mutation type (see Table 2.2-1), and sequence*period, where sequence corresponds to the order in which the subject received treatments, and a random effect for subject. No carryover term will be fit. In the case of the MFM percent outcome datasets for the adult only patients, the age group fixed effect term will not be included in the model. The LSMeans for the treatment groups will be calculated and provided, as will the estimated difference along with a 95% confidence interval for this difference and a formal hypothesis test that difference in the means is 0. Note that it is highly likely that some specific mutations will have insufficient subjects to fit the specified model. In that case a notation will be made in the relevant table(s) that there are not sufficient observations to fit the model.

Special care must be taken in crossover designs to ensure that there is no significant carryover effect; however, the pharmacological properties of amifampridine (an elimination half-life of 1.8-2.5 hours) are such that having a 12-day restabilization period will minimize any unequal carryover effects in the analysis.

Clinical Global Impression

CGI-S and CGI-I will be summarized by frequency tables and percentages for each sequence group and period. The values will be analyzed with a Wilcoxon rank-sum test as outlined in Putt and Chinchilli (2004). The treatment effects will be estimated using the Hodges-Lehmann estimator and a 90% asymptotic confidence interval.

Single Fiber Electromyogram

Summary statistics for mean jitter, median jitter, and percent block will be presented by treatment and visit. No formal inferential procedures will be performed for these data.

Slurp Test

Summary statistics for the time to slurp sound from the slurp test and its CFB (Day 0 for Period 1 and Day 21 for Period 2) will be presented. No formal inferential procedures will be performed for these data.

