^a RAW = observed data entered in the database; CFB = change from baseline = Value at timepoint - Baseline value.
 STATKING Clinical Services (yyyy-mm-dd)
 Source Program: xxxxxxx.sas

Table format repeats for PP population

Table 41. Summary of Treatment Emergent Adverse Events
 Catalyst Pharmaceuticals, Inc. - CMS-001
 Safety Population (N=xxxx)

	Amifampridine ^a	Placebo ^a
Patients With \geq 1 Treatment Emergent Adverse Event (TEAE)	xxx (xxx%)	xxx (xxx%)
Maximum TEAE Severity		
Mild	xxx (xxx%)	xxx (xxx%)
Moderate	xxx (xxx%)	xxx (xxx%)
Severe	xxx (xxx%)	xxx (xxx%)
Highest Relationship of TEAE to Treatment		
Not Related [n(%)]	xxx (xxx%)	xxx (xxx%)
Unlikely [n(%)]	xxx (xxx%)	xxx (xxx%)
Possible [n(%)]	xxx (xxx%)	xxx (xxx%)
Probable [n(%)]	xxx (xxx%)	xxx (xxx%)
Definite [n(%)]	xxx (xxx%)	xxx (xxx%)
Patients Who Discontinued Dosing Prematurely due to AE	xxx (xxx%)	xxx (xxx%)
Patients with \geq 1 Serious TEAE	xxx (xxx%)	xxx (xxx%)
Deaths	xxx (xxx%)	xxx (xxx%)

^a The denominator for all percentages will be the number of patients in the safety population.
 STATKING Clinical Services (yyyy-mm-dd)
 Source Program: xxxxxxx.sas

Page x of y

Table 42. Number and Percent of Patients with Treatment Emergent Adverse Events by System Organ Class and Preferred Term
 Catalyst Pharmaceuticals, Inc. - CMS-001
 Safety Population (N=xxxx)

Adverse Event Category ^b	Amifampridine ^a	Placebo ^a	Overall ^a
Total Number of TEAEs	xxx	xxx	xxx
Patients with \geq 1 TEAE	xxx (xxx%)	xxx (xxx%)	xxx (xxx%)
System Organ Class 1	xxx (xxx%)	xxx (xxx%)	xxx (xxx%)
Preferred Term 1	xxx (xxx%)	xxx (xxx%)	xxx (xxx%)
Preferred Term 2	xxx (xxx%)	xxx (xxx%)	xxx (xxx%)
System Organ Class 2	xxx (xxx%)	xxx (xxx%)	xxx (xxx%)
Preferred Term 1	xxx (xxx%)	xxx (xxx%)	xxx (xxx%)
Preferred Term 2	xxx (xxx%)	xxx (xxx%)	xxx (xxx%)

^a The denominator for all percentages will be the number of patients in the safety population.

^b Adverse events coded with MedDRA Coding Dictionary Version XXX.

STATKING Clinical Services (yyyy-mm-dd)

Source Program: xxxxxxxx.sas

Page x of y

Table 43. Number and Percent of Patients with Treatment Emergent Adverse Events
by Severity and System Organ Class and Preferred Term
Catalyst Pharmaceuticals, Inc. - CMS-001
Safety Population (N=xxxx)

Part 1 of 3
Treatment at Time of Onset = Amifampridine

Adverse Event Category ^a :	Mild ^b	Moderate ^b	Severe ^b
Total Number of TEAEs	xxx	xxx	xxx
Patients with ≥ 1 TEAE	xxx (xxx%)	xxx (xxx%)	xxx (xxx%)

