System Organ Class 1	xxx (xxx%)	xxx (xxx%)	xxx (xxx%)
Preferred Term 1	xxx (xxx%)	xxx (xxx%)	xxx (xxx%)
Preferred Term 2	xxx (xxx%)	xxx (xxx%)	xxx (xxx%)
System Organ Class 2	xxx (xxx%)	xxx (xxx%)	xxx (xxx%)
Preferred Term 1	xxx (xxx%)	xxx (xxx%)	xxx (xxx%)
Preferred Term 2	xxx (xxx%)	xxx (xxx%)	xxx (xxx%)

^a Adverse events coded with MedDRA Coding Dictionary Version XXX.

^b The denominator for all percentages will be the number of patients in the safety population.

STATKING Clinical Services (yyyy-mm-dd)

Source Program: xxxxxxxx.sas

Format repeats for Treatment at Time of Onset for Amifampridine, Placebo, and Overall.

Table 44. Number and Percent of Patients with Treatment Emergent Adverse Events
by Highest Relationship to Treatment and System Organ Class and Preferred Term
Catalyst Pharmaceuticals, Inc. - CMS-001
Safety Population (N=xxxx)

Part x of 3
Treatment at Time of Onset = Amifampridine

Adverse Event Category ^{a, b} :	Not Related	Unlikely	Possible	Probable	Definitely Related
Total Number of TEAEs	xxx	xxx	xxx	xxx	xxx
Patients with \geq 1 TEAE	xxx (xxx%)	xxx (xxx%)	xxx (xxx%)	xxx (xxx%)	xxx (xxx%)
System Organ Class 1	xxx (xxx%)	xxx (xxx%)	xxx (xxx%)	xxx (xxx%)	xxx (xxx%)
Preferred Term 1	xxx (xxx%)	xxx (xxx%)	xxx (xxx%)	xxx (xxx%)	xxx (xxx%)
Preferred Term 2	xxx (xxx%)	xxx (xxx%)	xxx (xxx%)	xxx (xxx%)	xxx (xxx%)
System Organ Class 2	xxx (xxx%)	xxx (xxx%)	xxx (xxx%)	xxx (xxx%)	xxx (xxx%)
Preferred Term 1	xxx (xxx%)	xxx (xxx%)	xxx (xxx%)	xxx (xxx%)	xxx (xxx%)
Preferred Term 2	xxx (xxx%)	xxx (xxx%)	xxx (xxx%)	xxx (xxx%)	xxx (xxx%)

^a The denominator for all percentages will be the number of patients in the safety population.

^b Adverse events coded with MedDRA Coding Dictionary Version XXX.

STATKING Clinical Services (yyyy-mm-dd)

Source Program: xxxxxxxx.sas

Format repeats for Treatment at Time of Onset for Amifampridine, Placebo, and Overall.

Table 45. Number and Percent of Patients Taking Concomitant Medications
 Catalyst Pharmaceuticals, Inc. - CMS-001
 Safety Population (N=xxxx)

Medication ^{a, b} :	Amifampridine	Placebo	Overall
Total Number of Concomitant Medications	xxx	xxx	xxx
Patients Taking \geq 1 Concomitant Medication	xxx (xxx%)	xxx (xxx%)	xxx (xxx%)
ATC Level 4 Term 1	xxx (xxx%)	xxx (xxx%)	xxx (xxx%)
Preferred Term 1	xxx (xxx%)	xxx (xxx%)	xxx (xxx%)
Preferred Term 2	xxx (xxx%)	xxx (xxx%)	xxx (xxx%)
ATC Level 4 Term 2	xxx (xxx%)	xxx (xxx%)	xxx (xxx%)
Preferred Term 1	xxx (xxx%)	xxx (xxx%)	xxx (xxx%)

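### The planned adverse-event tables would count open-label re-stabilization under amifampridine, setting about 21 days (20 to 22) of exposure against 8 on placebo

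*SAP*

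**What the plan says.** SAP 5.0 states that a treatment-emergent adverse event "is any AE that occurs after the start of treatment. All TEAEs will be summarized by the treatment at the time of onset". Protocol 15.3 has the same attribution rule: TEAEs "will be summarized by the treatment at the time of onset". Neither document says whether treatment starts with the first run-in dose or the first randomized dose. Neither says where events with onset during open-label treatment are tabulated.

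In SAP Appendix B, Table 41 has Amifampridine and Placebo columns, and Table 42 adds Overall. For Tables 43 and 44 the shell note reads "Format repeats for Treatment at Time of Onset for Amifampridine, Placebo, and Overall". In all four tables, "The denominator for all percentages will be the number of patients in the safety population".

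Between the blinded periods all continuing patients take open-label amifampridine. Protocol 10.1 says: "After Day 8 in-clinic evaluations, patients will return to open-label study drug, through Day 21". The documents give three lengths for this interval:

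- 13 days by the labels Days 9 to 21;
- 14 days in SAP 1.2 ("patients will return to open-label amifampridine phosphate for 14 days between Periods 1 and 2"), the Protocol synopsis, and Protocol 13.4 (as two weeks);
- 12 days in SAP 4.2.1 ("having a 12-day washout period should minimize any unequal carryover effects") and SAP 4.2.2 ("having a 12-day restabilization period will minimize any unequal carryover effects in the analysis").

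**The concern.** Protocol 9.1 lists safety and tolerability relative to placebo as the first primary objective, and Protocol 15.2 makes the safety analysis descriptive. The crude percentages in Tables 41 to 44 are therefore the comparison a reader will see. The randomized crossover provides equal blinded time on each treatment. The planned tables lose that balance by adding a longer unblinded stretch to one side only.

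The distortion can run either way. Longer follow-up alone can create an apparent amifampridine excess. It can also hide an excess on placebo. That second possibility matters here, because Protocol 8.5 describes a withdrawal design in which patients are expected to worsen on placebo, and Protocol 11.1 counts worsening of a pre-existing condition as an adverse event.

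**Working it through.** **Period lengths (inclusive day counts).** Period 1 is Days 1 to 8: 8 − 1 + 1 = 8. Period 2 is Days 22 to 29: 29 − 22 + 1 = 8. Both reproduce the 8 days stated in the protocol. Re-stabilization is Days 9 to 21: 21 − 9 + 1 = 13, which matches neither the stated 12 nor the stated 14. I therefore carry D = 12, 13 and 14.

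**Exposure after randomization, per completer.** Amifampridine days = 8 + D; placebo days = 8; open-label share = D/(8 + D).

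| D | Amifampridine days | Ratio to 8 | Open-label share |
|---|---|---|---|
| 12 | 20 | 2.50 | 0.60 |
| 13 | 21 | 2.63 | 0.62 |
| 14 | 22 | 2.75 | 0.64 |

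This is a floor. SAP 1.2 starts amifampridine dosing on Day 1 of run-in, and Protocol Table 3 (footnote n) starts non-serious event reporting that day. If run-in counts, a 7-day run-in gives 27 to 29 days (ratio 3.4 to 3.6) and a 28-day run-in gives 48 to 50 days (ratio 6.0 to 6.25). The +1 day windows and the exact dose of each switch move these counts by about a day at most.

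**What this could do to the percentages (illustration).** The documents give no adverse-event rates for this trial, so these inputs are assumptions. Let p be the 8-day incidence of at least one event under blinded amifampridine, with constant daily hazard, and let r be the open-label hazard divided by the blinded hazard. Incidence in the Amifampridine column = 1 − (1 − p)^((8 + D·r)/8).

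Suppose there is no true difference, so placebo incidence is also p. For D = 13:

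| r | p = 10% (ratio) | p = 20% (ratio) |
|---|---|---|
| 1 | 24.2% (2.42) | 44.3% (2.22) |
| 0.5 | 17.4% (1.74) | 33.3% (1.66) |
| 0.25 | 13.8% (1.38) | 26.9% (1.35) |
| 0.1 | 11.5% (1.15) | 22.8% (1.14) |
| 0 | 10.0% (1.00) | 20.0% (1.00) |

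Example: r = 1, p = 10% gives 1 − 0.9^(21/8) = 0.242. Over D = 12 to 14 the ratios are 2.1 to 2.5, 1.6 to 1.8, 1.3 to 1.4 and 1.1 to 1.2 for r = 1, 0.5, 0.25 and 0.1.

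**Masking a placebo excess.** Assume a true 8-day incidence of 10% on amifampridine and 20% on placebo. With D = 13 the table would show 24% against 20% (r = 1), 17% against 20% (r = 0.5) or 14% against 20% (r = 0.25). The order reverses once the amifampridine column holds 8 × ln 0.8 / ln 0.9 = 16.94 blinded-equivalent days, that is when r exceeds (16.94 − 8)/D = 8.94/D: 0.75, 0.69 and 0.64 for D = 12, 13 and 14.

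**Blinded periods only.** 8 amifampridine days against 8 placebo days, ratio 1.0.

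**The case against.** The strongest reply is that the SAP never actually says open-label events go under amifampridine. Treatment could mean the two crossover arms only; SAP 5.0 tabulates concomitant medications by the treatment given in the study period, and the Table 5 shell numbers only Periods 1 and 2. On that reading the imbalance does not arise. But the adverse-event rule is worded differently from the medication rule. It covers all TEAEs and goes by treatment at onset, and an event starting on Day 15 starts on amifampridine. If only blinded periods were meant, open-label events would have no column at all and the SAP would still need the same edit.

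Several other points carry weight:

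- The range of 20 to 22 days applies after randomization and is a minimum.
- The incidence figures rest on assumed rates and constant hazards, and they ignore rescue dosing and visit-based ascertainment. They show direction and plausible size, not a prediction.
- The objective also covers overall safety, which all-exposure counts serve. A separate open-label column keeps that information.
- Data Listings 3 and 13 give event dates and treatment dates, so a reader could rebuild a blinded-only count apart from switch-day events. A comparison serving a primary objective should not depend on that.

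**Conclusion.** The concern holds. Following the stated rule and the shells gives an unbalanced and mostly open-label comparison: 20 to 22 days against 8 per completer after randomization, and more if run-in counts. The exposure figures need no assumed event rate; they rest on the day counts and on attribution by treatment at onset. The size of the effect on the percentages is unknown. It ranges from none, if few events start during re-stabilization, to roughly a doubling of the crude ratio if the open-label and blinded hazards are equal. The primary efficacy test is unaffected, but the plan should be changed because this is the comparison offered for a primary objective.

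A separate reporting gap, which does not bias the placebo comparison, is that SAP 2.2 limits the safety population to randomized patients while Protocol 15.2 includes everyone dosed. Events in patients dosed in run-in but never randomized would be missing from Tables 41 to 44 and from Data Listing 3.

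**What to change.** 1. In SAP 5.0, define the start of treatment for TEAEs.
2. In Tables 41 to 44, make the comparison double-blind amifampridine against double-blind placebo, limited to onset in Period 1 or 2. Use as denominator the patients dosed with that treatment in a blinded period.
3. Report run-in and re-stabilization events in a separate open-label column. This keeps Protocol 15.3's attribution rule.
4. State a rule for onset on the switch days (Days 0, 8 and 21/22), because Data Listing 3 shows dates without times. One option is to assign the event to the treatment taken at that visit, since the new treatment begins only with the next scheduled dose (Protocol 13.2 to 13.4), and to show the opposite assignment as a check. Protocol 10.1 places the Period 2 switch after the Day 22 assessments and Protocol 13.4 after the Day 21 assessments; these must be reconciled first, as must the 12-, 13- and 14-day lengths.
5. Separately, reconcile SAP 2.2 with Protocol 15.2 so that events in patients dosed but not randomized appear in the open-label column and in Data Listing 3.

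The cost is SAP text, one added column in Tables 41 and 42, one added part in Tables 43 and 44, and revised denominators. Step 5 also needs a place for patients who have no sequence. No new data are collected, and a few switch-day events will be assigned by convention.
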